Research nurses will conduct face-to-face assessments and surveys with participants at baseline, 3 and 6 months post-baseline. Feasibility and acceptability measures of the intervention will be collected across the study. We will also conduct two evaluative focus groups with a purposively selected subsection of the intervention group (n=8 per group) to obtain perspectives on perceived outcomes and utilization of behavioral strategies from the intervention and the feasibility and acceptability of the technologies. (See Figure 2).

Procedures / Data Collection and Management. CAB. The community advisory board (CAB) will trial *Lose-It Premium*, including the social comparison group page, during study months 1-6 to identify potential areas in which male subjects may need additional instruction, facilitation, and ongoing support. The investigative team will discuss the CABs feedback and the PI will keep reflective research notes tracking decision-making processes. The CAB will also review the text message library to ensure message content is locally relevant and meaningful prior to intervention dissemination.

Rural Male Subjects. Two trained research nurses will conduct the assessments and will be flexible in working hours that match participants availability. The baseline visit will take approximately 90 minutes to complete. Men will complete questionnaires and have their blood pressure, weight, and resting heart rate assessed. Those men exhibiting risk that may contraindicate increasing physical activity or weight loss will be referred to their

primary care provider for written clearance to participate.⁹⁹ All questionnaires and biomarkers will be entered into a secure site through the Internet. All data will be entered in the REDCap server. The UNMC Research IT Office instructs investigators in its use and hosts the REDCap database of project data.

Baseline Instructions Provided to Both Groups. Each man will receive his *Lose-It* user ID and password, as well as written instructions to access the research nurse, and information about technical support. Temporary emails will be set up for each subject that contain no personal identifiers (ie. [contact]). These email accounts will be used only for the purpose of setting up a *Lose-It* account and receiving automated *Lose-It* account reports. No personal communication with subjects will happen through these email accounts. At baseline, both groups will receive an informational packet with verbal instruction focused on a lifestyle change plan for healthy eating and activity to accomplish weight loss. Our goal is that the participants will demonstrate a weight loss of 5% or more of their baseline body weight, which is the minimum weight loss documented to produce a decrease in health risks (diabetes, cardiovascular disease, hypertension).¹⁰⁰⁻¹⁰¹.

Smartphone Use: Each subject will be asked to wear their smart phone during waking hours on their hip or in a pocket.

Nutritional Plan: Recommended approaches for achieving negative energy balance through reduced caloric intake and increasing physical activity to recommended levels will be provided with the primary goal of losing 1-2 pounds a week during the 3 month intervention. Participants caloric eating plan goals will be calculated by the *Lose-It* app based on their age, gender, height, and activity level tracked in the app.

Physical Activity Plan: Current recommendations from public health agencies and scientific organizations including the NHLBI,¹⁰² DHHS/CDC,^{103, 104} and the ACSM^{104, 105} outline physical activity as an important part of weight management. Participants will be advised to gradually meet minimal targets 10,000 steps per day (goal PA outcome on *Lose-It* apps) and 150 minutes a week of moderate-intensity or greater activity.

Daily Self-Weighing: Participants will be provided instructions for measuring and recording their weight daily. All participants will be 1) oriented to the text messaging process, 2) respond to a test text message to ensure receipt. Participants will receive an orientation, with written instructions and physical demonstration, to *Lose-It* Basic app. Instructional content will include how to post nutritional intake, recording physical activity and weight. Participants will be asked to wear their smart phone during waking hours over the next 26 weeks to input their dietary intake and track physical activity, and record their self-measured weight daily. Assessment visits at 3 and 6 months post-baseline will evaluate the participants change in biomarkers, self-report scales, and ongoing engagement with the *Lose-It* app and other health technologies. Each man will make an appointment for his next reassessment at the end of each visit. The nurse will text a visit reminder 2 weeks prior to the next appointment.

Additional Instructions for MT+. At the conclusion of the baseline visit, those participants randomized to the MT+ group will be given instructional training with demonstration for use of the 1) Nokia Body+ Wi-Fi scale, 2) instructional picture booklets demonstrating correct setup and use of the Wi-Fi scale ¹⁰⁶and the *Lose-It* Premium version app features, and 3) a technology support phone number. The GA will call the men within two days of their baseline visit to verify their success in using these feature and answer any questions. Investigators will monitor app usage statistics for MT+ participants daily and a GA will provide reminder prompts via text message, followed by phone call, when non-adherence is observed for greater than 5 days. Participants can also contact research staff for technical support via phone. Remind.com will be used to send the text messages. Remind.com provides free text messaging to any smartphone device through SMS and doesn't require app download. MT+ participants will receive a text message at 8:00am throughout the 3-month intervention period. MT participants will only receive a text reminder related to their next assessment point appointment by the research nurse.

Lose-It Account Retention Option for Subjects at end of Study: As subjects have matriculated through our study, many have requested their desire to retain their Lose-It account food log and physical activity data. Because we set up the accounts using dummy username and passwords- the men are not able to retain their log information in Lose-It (basic or premium accounts) unless we conduct a username and password change of ownership. We consulted with our community advisory board members on 1-14-19- whom

were in full support of offering subjects an option to change ownership of their Lose-It account upon study completion. We have written and tested a procedure for changing username and password (See Protocol for Lose-It accounts at the end of the study document) that will permit the subjects to select/input a password that is not known to us which will ensure the privacy of their Lose-It account after the time of password change. We will inform the subjects of this option for change of ownership at their 6-month visit, at which time a revised written consent will be obtained. For those subjects who have already completed the six month visit, we will contact them by text and email informing them of the option. Those completers who desire this option will be provided a telephone call during which an electronic version of the revised written consent will be obtained (as consistent with our procedures for obtaining informed consent at point of enrollment).

Focus Groups. Two evaluative focus groups will be held at 6 months post-baseline with a purposive sample of intervention group completers stratified according to their weight loss outcome (successful/unsuccessful in achieving 5% baseline body weight loss) to solicit their perceptions on the MT+ intervention efficacy, including acceptability/feasibility.¹⁰⁷ Use of two focus groups permits cross-case comparative analysis of the intervention.^{70, 108} Focus group participants will receive \$25 for their attendance and will be asked to maintain confidentiality of the contents of the focus group discussion. The 90-minute focus groups will be held at the same community center as the assessments and audio recorded. The PI, an experienced focus group moderator, will lead the discussion with a semi-structured interview guide informed by the tenets of the social ecological perspective and study aims. The focus group

questions will be pretested by the honors research students, who will also serve as scribes during the focus groups, noting non-verbal expressions/gestures, interactions, and other impressions that occur during the group discussion. Questions will be aimed at eliciting the men's experience and perceptions: How did you find the experience of tracking your eating, activity, and weight with the *Lose-It* app?, How did you find the experience of participating in a group comparison page with other study participants? Immediately after the interviews, the moderator and scribes will write reflective notes as to the groups interaction, which created/sustained the descriptive detail shared and provide peer-debriefing. The audio files will be transcribed verbatim. Collectively, the interview transcript, peer-debriefing, and reflexive memos will create a decision trail which will serve as an audit trail to demonstrate accountability.¹⁰⁹ Audio recordings will be deleted after being used to assure the accuracy of written transcripts during analysis.

Variable * Measure Description (Data Collection Time Points)
Baseline & Screening

PAR-Q17 (S**) PAR-Q17, Physical**

Activity Readiness

Questionnaire- ACSM

Recommended 88-90

(Baseline)

Demographic (S****) **Demographic-** (e.g.,
race, gender, age,
education, marital
status, occupation)-

from

CENTRIC(Baseline)

Aim 1 Feasibility and Acceptability

Fidelity (F*) Component Specific Fidelity Check-list-**

Design, Training, Delivery, Receipt, Enactment.

Checklist from previous study 92 **(Baseline, 3, 6
mo.)**

Recruitment / Retention (O*) Weekly monitoring of recruitment and retention
counts (frequencies and percentages, PI

research notes specifying recruitment and
retention strategies/outcomes **(weekly)**

SM Adherence (CO**) Calculated as the % of actual number of days
data entered over 1 week- from Tsai et. al
study 91 **(weekly)**

Health ITUES Survey(O*) **Health Information Technology Usability**

Evaluation Scale (Health ITUES) Impact

subscale (3 item) Perceived Usefulness

subscale (12 item)- adapted from Schnall
study **(3, 6 mo.)**

Acceptability and Feasibility of SMS (O*) **SMS Survey**- from [name] et al study 6 **(3
mo.)**

Two Evaluative Focus Groups (MT+) (O*) Semi-Structured Interview questions (guided by
aims 1,2, and social ecological perspective) with

probes Participants perceptions of the intervention experience (i.e. perceived efficacy, behavioral strategies, challenges with adherence, satisfaction with technology) **(6 mo.)**

Aim 2- Preliminary Efficacy

Fruit and Vegetables Servings (O*) **BRFSS -Fruit and vegetable dietary intake module (6 items)**- CDC- moderate validity and reliability93 **(Baseline, 3, 6 mo.)**

Sugar-Sweetened/ Total Beverage Energy Intake (O*)

Brief Questionnaire to Assess Beverage

Intake (BEVQ-15)- Cronbach's a ranged .97 to .99, significantly correlated with three 24-hour dietary recalls94 **(Baseline, 3, 6 mo.)**

Report of Daily Log of Dietary Intake, PA, and Weight (O*)

Lose-It app programmed to send automatic daily reports to researchers- Protocol from previous study using *Lose-It* app43 **(weekly)**

Physical Activity (O*) **BRFSS- Physical activity module (7 items)**- CDC- moderate validity and reliability95 **(Baseline, 3, 6 mo.)**

Weight (O*) **Tanita Scale (TBF-300)**- Tanita model manufacturer instructions [TBF-300, Tanita Corporation of America] **(Baseline, 3, 6 mo.)**

Nokia Body+ Wi-Fi Scale- Nokia model manufacturer instructions **(MT+ group-daily)**

Blood Pressure (O*) Protocol outlined by Perloff et al.96 **(Baseline, 3, 6 mo.)**

Resting Heart Rate (O*) Protocol outlined by Perloff et al.96 **(Baseline, 3, 6 mo.)**

Aim 3 Indicators of Community Capacity

Community Partners Profile (S****) Demographic Form (community location, leadership role, characteristics- Demographic Form from [name] et al.6 **(Baseline)**

Community Capacity (O*) **Community Capacity Evaluation Survey (Baseline, 12, 24, 36 mo.)**- from previous study97 for measures on dimensions of communication, trust, participation and influence, leadership, community power, collective efficacy, accomplishments and impact, group roles, participatory decision-making procedures, resource mobilization, sustainability, partnership linkages, and overall satisfaction.

PIs research notes / audit activities reports/logs / CAB

minutes / Student questionnaire: CAB- Tracking of participation level of members in recruitment/retention strategies (i.e. # meetings, activities, resources allocated, partnership/network linkages, leadership roles assumed, participatory-decision-making), member attrition with reasons, perceived benefits/skills gained, barriers and facilitators of retention, proposed strategies to increase

retention. STUDENTS- log of community outreach activities, implementation time, and outcome, Questionnaire evaluating perceived community outreach skill (identify, engage, evaluate, leadership) administered pre-post clinical rotation, GA/Honors students activity log, dissemination events.

After providing informed consent, the men will be oriented to the ActiGraph GT9X by the research nurse. The men will be instructed to wear the ActiGraph GT9X on their right hip continuously for seven days^{5,6,7}, only removing the device for bathing. Subjects will also be provided with written instructions for device use in addition to the hands-on demonstration, a troubleshooting number, an activity questionnaire to capture recreational and vocational activity, and postage-paid return envelope. After wearing the device for seven days, the men will mail the device back to the UNO investigators, Drs. [name] and [name]. Those men who return the device as indicated will be issued/mailed a \$25.00 incentive for their participation. Phone and text reminders will be sent to subjects on the eighth day (the day after completing the 7-day testing) reminding them to return their ActiGraph by our GA. Those men not returning the Actigraph after the phone and text reminder will be sent a mailed letter encouraging them to return the device with a reminder that failure to return the device will result in no incentive received for their participation.

Analysis: Accelerometers that contain a minimum of five 10-hour days, including both weekday and weekend days, of tracking will be eligible for analysis^{7, 8}. Our collaborating investigators-UNO biomechanical engineer, [name], and Information Science and Technology Specialist, [name], will supervise the advanced analyses of our ActiGraph data with their UNO graduate students across four forms: 1) Traditional ActiGraph analysis (raw accelerations and step counts per 15 second bouts, 2) Custom bout and sedentary analysis, 3) Nonlinear activity pattern analysis, and 4) Applying deep-learning and advanced analytics^{5,9}. Subjects who participate in this sub-study will be mailed a single-page, individualized, easy to read, plain language, graph report containing their peak activity and sedentary times, as well as a report of minutes of minimum, moderate, and vigorous physical activity from their 7-day measurement period. Subjects will be given the same troubleshooting number to call if they have any questions regarding interpreting this individualized physical activity report.

Statistical Analysis

Descriptive statistics will be calculated on all variables, including frequencies and percentages for recruitment/retention, demographic, and categorical variables. Means and standard deviations will be calculated for all continuous variables and measures at each time point. Feasibility and acceptability analyses for aim 1 are largely descriptive, as we will be assessing participation rates and percentages of eligible men and which were the more effective recruitment methods. Qualitative content analysis, as described by Hsieh and Shannon (110) will guide interpretation of the focus group findings from the intervention participant groups. The interview transcript, reflective memos and observation notes taken during each focus group will

comprise one unit of analysis for within/across case comparison. The topics outlined by semi-structured interview guide will be extracted and organized. The researcher will read the transcripts for substantive coding. Data facts will be organized under a priori coding categories. The categories are named a priori because they are built into the interview guide questions. A data fact will be defined as those data elements that recurred in the interview without lack of consensus or were least participant to errors in inference (111). All data provided in a response to each question will be coded together. Incomplete, competing, or alternative topics that present in the discussion but were not identified a priori will be aggregated by the researcher and examined to determine their fit with the purpose. These topics will be compared with the synthesized findings to challenge alternative explanations and unnoticed flaws in the researchers argument.(112). A data matrix will be used to display the coded data to search for patterns across coding categories. The PI and honors students will return to the data to explore patterns further, supporting iterative analysis. Data categories will be re-contextualized into an account that makes sense for the entire studys data set. Meaning, the findings are integrated to provide new understanding or explanation to the interpretation of the intervention outcome data (112). Peer-debriefing and audit checking will occur weekly across the analysis by the PI and GA to assure accuracy of the findings.

Aim #2: Determine preliminary efficacy of a MT+ intervention to a comparison group receiving only a basic self-monitoring app (MT) in achieving 1) weight loss (primary), and 2) improved diet and increased PA (secondary) at 3 months post-baseline and follow-up at 6 months post-baseline in rural men. The efficacy analyses for aim 2 will be tested via RM-ANOVA models, as they provide a direct measure of differences between the intervention and comparison groups in weight loss and dietary and PA behaviors across the study, as well as effect size estimates. Huynh-Feldt corrected F-tests will be used in order to account for any possible violation of sphericity. If there is a higher than expected attrition rate, a maximum likelihood estimation method (e.g. mixed models) will be used instead of RM-ANOVA in order to utilize all available data and not delete cases in a listwise manner. Overall weight lost at follow-up will be assessed via an independent groups t-test. Outcome variables that are not normally distributed will either be transformed or assessed with nonparametric methods.

Aim #3: Determine quantitative and qualitative indicators of community capacity (resource mobilization, learning opportunities-skills development, partnership linkages, participatory decision- making, leadership) to support a relevant weight loss intervention for rural men. For aim 3, multiple indicators of community capacity will be used to evaluate support for the weight loss intervention applying best practice recommendations (113), 1) CAB- assessed community capacity change survey report by CAB, participation level of members (i.e. # meetings, activities, resources allocated, partnership/network linkages, leadership roles assumed), member attrition with reasons, Qualitative indicators of community capacity in CAB include perceived benefits/skills gained, barriers and facilitators of retention, proposed strategies to increase retention, CAB evaluation of student outreach activities, 2) STUDENTS- clinical log of community outreach activities (type, number, hours) developed, implemented, and outcome,

leadership activities (dissemination via honors projects, clinical conference and class presentations). Qualitative indicators of community capacity among students will include perceived skill development, and leadership confidence. Graduate level students help in training sessions, data collection and implementation of intervention.

3) PARTICIPATORY DECISION- MAKING as an indicator of community capacity will be evaluated via CAB survey and tracked ongoing through study. PI research-field notes will record student-engaged activities and time points.

SubStudy Aim: To determine the feasibility among a convenience sample of rural men currently enrolled in our Rural Men's health study to wear the Actigraph GT9X (single wearable sensor) for seven continuous days to measure their physical activity among the total volume of activity bouts across three gait dimensions: intensity, symmetry, and variability.

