A total of 8-10 community advisory board members (CAB), 42 student nurses from the UNMC Northern Division NRSG 413 Population Centered Care course, and 80 rural male subjects (40 per group) are needed to achieve the proposed objectives. The sample will consist of 80 men (40/group) who meet the inclusion criteria. Hertzog 74suggested that 30 participants per group in a pilot study is a sufficient sample size for aims involving between group differences and if the results are to be used to estimate the needed sample size for a future, fully- powered study. It is important for this study that we obtain reliable estimates of effect size with which to perform a power analysis for subsequent research, so 40 participants per group will be sought, for a total of 80. Some participants will likely not complete the study, so we will enroll 80 men to allow for up to a 30% attrition rate. Power for the repeated measures analysis of variance (RM-ANOVA) was determined using G*Power 3.1.9. A within-between interaction will be the primary test of significance (time*group interaction). Assuming a small effect size ($f=.10$),⁷⁵ a significance level of .05, 3 time points, and an estimate of .5 for the correlation between time points, 164 participants (82 per group) would be needed to have 80% power. Because this is a pilot study, a smaller sample size is justified, and the results of the pilot study will be used to update the power analysis prior to a future study.

Purposeful justification for the total number of community advisory board members and student nurses is based upon their information rich knowledge of the rural context as either community leaders or students in a rural college of nursing. Justification of the total sample size desired for the community advisory board is based upon optimal group function / interaction (8-10 persons) documented in previous advisory board work in agricultural based locales (Kingman, Yoder, Hodge, Ortega, & Field, 2004). Justification for inclusion of 42 student nurses was based upon the aim of the R-15 AREA NIH mechanism to expose undergraduate students to research. Community outreach is a concept taught in NRSG 413- Population Centered Care. It was deemed feasible to involve all students enrolled in this NRSG 413 course to the community outreach activity of this study- without excluding any student.

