UNMC Northern Division Student Nurses Enrolled in NRSG 413- Population Centered Care course receive training in community outreach / community engagement as an expected course outcome. Students in this course will spend 2 hours of their assigned course clinical time in group discussion with the principal investigator, [name], who is an advanced practice public health nurse. The discussion will involve planning community outreach and community engagement strategies for our study region that may enhance recruitment and retention of CAB members and subjects. Students will be asked to identify strategies for enhancing the planned community outreach and community engagement specific to rural populations for this study. Activities will include determining strategic recruitment material dissemination, creating community resource maps, and identifying community leaders and lay persons pivotal to enhancing community partnership. Prior to beginning the discussion, students will be asked to complete a short survey about their understanding of the public health nurse role in community outreach / community engagement. The students will be asked to complete the same survey post discussion to determine if the discussion experience enhanced their understanding of this role.

Intervention: The proposed feasibility study is a pragmatic RCT. Rural men (ages 40-69) will be recruited over a 12 month period to obtain a target enrollment of 80 subjects. Subjects will either be allocated to the intervention (Lose-It Premium with social comparison group, Wi-Fi scale for self-monitoring, plus SMS support messages for weight loss- MT+) (n=40) or the comparison group (Lose-It Basic- MT) (n=40). These group sizes reflect oversampling by 30% in each group to allow for attrition, based upon attrition rate averages.

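### Forty men per arm is justified as giving a reliable effect size for powering the next trial, but the estimate will carry about ±0.45 to ±0.53 SD, roughly as much as the effect planned for

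*Combined protocol and SAP*

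**What the plan says.** The Accrual section cites a rule that "30 participants per group in a pilot study is a sufficient sample size for aims involving between group differences". It then says it is important that "we obtain reliable estimates of effect size with which to perform a power analysis for subsequent research", and continues "so 40 participants per group will be sought, for a total of 80". Reliability of the effect size is therefore the stated reason for 40 rather than 30 per arm.

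On losses, the same section says "we will enroll 80 men to allow for up to a 30% attrition rate". The Intervention paragraph under Methods says "These group sizes reflect oversampling by 30% in each group to allow for attrition".

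The Accrual section also gives a formal calculation for the time-by-group interaction in a repeated-measures ANOVA. With f = .10, alpha .05, three time points and correlation .5, 164 men would be needed for 80% power. It accepts a smaller sample because this is a pilot, and ends by saying that "the results of the pilot study will be used to update the power analysis prior to a future study".

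Statistical Analysis, Aim #2, plans effect size estimates from the ANOVA and an independent-groups t-test of weight lost. No section gives a target interval width, or a rule for allowing for uncertainty when the pilot effect is carried into the next calculation.

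**The concern.** The point is not that a pilot is small or underpowered; the plan says so itself. The plan claims a specific property for this sample size, that the effect estimate will be good enough to power later research, and that claim can be checked.

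If the estimate is too imprecise, a next trial sized on it will be too small when the pilot overestimates by chance, and oversized or abandoned when it underestimates. The Background and Rationale section presents that next trial as the purpose of this one.

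**Working it through.** **1. The plan's own figure.** For the within-between interaction with 2 groups and 3 time points, λ = f²·N·3/(1 − ρ) = 0.01·N·3/0.5 = 0.06·N, with df 2 and 2(N − 2). Power is 0.7998 at N = 162 and 0.805 at N = 164. The stated 164 reproduces exactly and is not disputed. On the same inputs, power is 0.48 at N = 80 and 0.35 at N = 56.

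**2. Completers per arm.** There are 40 with no loss and 40 × 0.70 = 28 at the full 30% loss. Reading the 30% as oversampling gives 40/1.3 = 30.8. The loss reading ends below the cited 30.

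**3. What f = .10 means in SD units.** The documents give no SD in kg, so I work in SD units. With ρ = .5 the SD of change is √(2(1 − .5)) = 1 raw SD. With an arm difference of d, f is the root mean square over visits of the centred half-differences.
- Pattern 0, d, d: f = d/√18 = 0.2357d, so d = 0.42.
- Linear pattern 0, d/2, d: f = 0.2041d, so d = 0.49.

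The time pattern is my assumption. If half of a 3-month effect were lost by 6 months, f = .10 would mean 0.49 at 3 months and only 0.24 at 6.

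**4. Precision.** SE(d) = √(2/n + d²/(4n)); half-width = 1.96·SE.

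| n per arm | SE at d = 0.5 | Half-width at d = 0.5 | 95% CI at observed 0.42 |
|---|---|---|---|
| 40 | 0.227 | 0.445 | −0.02 to 0.86 |
| 28 | 0.271 | 0.532 | −0.11 to 0.95 |

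Exact noncentral-t intervals agree to within about 0.01. At 31 per arm the half-width is 0.51.

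Adjusting for baseline multiplies the width by √(1 − .5²) = 0.866, about 13% narrower: 0.445 × 0.866 = 0.385 and 0.532 × 0.866 = 0.461. An observed 0.42 would then give about 0.04 to 0.80 (n = 40) or −0.04 to 0.88 (n = 28).

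**5. Consequence for the next trial.** This step assumes that the observed d is used as it stands, in n = 2·((1.96 + 0.8416)/d)² per arm for 80% power.
- True power falls below 60% when the observed d exceeds 2.8016/(1.96 + 0.2533) = 1.266 times the true d.
- The size is within a factor of two when the observed d lies between d/√2 and d·√2.

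| True d | n per arm in pilot | Next trial below 60% power | Within a factor of two |
|---|---|---|---|
| 0.30 | 40 | 36% | 36% |
| 0.30 | 28 | 38% | 31% |
| 0.42 | 40 | 31% | 49% |
| 0.42 | 28 | 34% | 42% |

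Worked case (d = 0.42, n = 40): the threshold is 1.266 × 0.42 = 0.532, and (0.532 − 0.42)/0.226 = 0.49, giving 31%. Simulation gives the same figures to within one percentage point.

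**6. Same check in the plan's own metric.** If the true f is .10 and N = 80, the 10th to 90th percentiles of the total N implied by the observed f are about 58 to 518, against 164, and 59% of pilots imply too few.

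**7. What the pilot estimates better.** The 95% limits for the SD are 0.86 to 1.19 times the estimate at 40 per arm, and 0.84 to 1.23 times at 28. Sample size goes with SD², so at 40 per arm the error in n from this source is about 0.75 to 1.41 times.

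**The case against.** The plan is candid. It calls the trial a pilot and the efficacy aim preliminary, and it states the 164 men that a powered test would need. It cites a source for 30 per group, which could not be examined here. It commits only to updating a power analysis, not to plugging in the observed effect. A conservative use would do much better: sizing on a one-sided 80% lower confidence limit cuts the share below 60% power to about 13% at a true 0.3 SD with 28 per arm. All of that stands. But disclosing low power does not make the estimate reliable, a rule of thumb is not a precision statement, and the plan sets out no conservative rule.

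Four stronger readings are tempting, and the documents do not support them.
- *The pilot cannot tell no effect from a large one.* It can. An observed 0.8 SD gives 0.26 to 1.34 even at 28 per arm, and an observed zero gives ±0.52, which excludes 0.8.
- *The next trial would often be underpowered even at a true 0.5 SD.* The unconstrained shares are 31% (n = 28) and 28% (n = 40). However, they require a next trial of fewer than about 40 per arm. The Summary and the Background describe it as larger than this one, and with at least 40 per arm both shares are zero. The shares at 0.3 and 0.42 SD do not change under that floor.
- *28 completers per arm is the expected number.* It is the worst case of an upper bound on attrition.
- *The 5% figure supplies the difference to power on.* Under Baseline Instructions Provided to Both Groups, "a weight loss of 5% or more of their baseline body weight" is a goal for each participant in either arm, not a difference between arms.

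**Conclusion.** The concern holds for the reliability claim and its intended use. The half-width of 0.45 SD, or 0.53 SD at worst-case attrition, follows from the planned numbers alone and hardly depends on the true effect. It is about the size of the effect implied by the plan's f = .10, so no effect and a small-to-moderate effect cannot be told apart dependably. Baseline adjustment, which the plan does not specify, moves the limits slightly without changing this.

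The mis-sizing figures (31% to 38% of next trials below 60% power; 31% to 49% within a factor of two) are conditional. They rest on an assumed true effect of 0.3 to 0.42 SD and on face-value use of the observed effect. Allocation, analysis and participants in this trial are unaffected. What lacks support is the stated justification for 40 per arm and the planned use of the effect size.

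**What to change.** In the Accrual section:

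1. Remove the claim of reliable effect-size estimates. State instead that 40 per arm gives a 95% half-width of about 0.45 SD for the between-arm difference in weight change, or about 0.53 SD if 30% are lost, and that the observed effect will be reported with its 95% confidence interval.
2. State that the pilot will supply the SD of weight change, the between-visit correlation, retention and adherence, each with a confidence interval.
3. Replace the closing sentence on updating the power analysis. The next trial would be sized either on a worthwhile between-arm difference fixed in advance, or on a conservative confidence limit of the pilot effect, with the limit named. A between-arm difference could be in the proportion of men reaching 5% loss or in mean percentage weight change. It must be defined explicitly, because the 5% goal does not define it.

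The cost is a rewording of a few sentences and a less favourable claim for the pilot. Recruitment, visits and analyses stay as they are.
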